## 6.2 Inclusion Criteria

Each subject must meet all of the following criteria to be enrolled in this study:

- 1. Written and signed informed consent must be obtained before any protocol specific assessment is performed.
- 2. Male or female, aged 18 years or older.
- 3. Has at least 3 of the following symptoms:
  - Cough
  - Production of purulent sputum
  - Dyspnea (shortness of breath)
  - Pleuritic chest pain
- 4. Has at least TWO of the following abnormal vital signs:
  - Fever or hypothermia documented by the investigator (temperature > 38.0°C [100.4°F] or < 36.0°C [95.5°F])
  - Hypotension with SBP < 90 mm Hg
  - Heart rate > 90 beats per minute (bpm)
  - RR > 20 breaths/minute
- 5. Has at least 1 clinical sign or laboratory finding associated with CABP:
  - Hypoxemia ( $PaO_2 < 60 \text{ mm Hg by ABG or oxygen saturation} < 90\%$  by pulse oximetry)
  - Physical examination findings of pulmonary consolidation (eg, dullness on percussion, bronchial breath sounds, or egophony)
  - An elevated total white blood cell (WBC) count (> 12,000 cells/mm^3) or leucopenia (WBC < 4,000 cells/mm^3) or elevated immature neutrophils (> 15% band forms) (regardless of total peripheral WBC count)
- 6. Has disease categorized as being PORT Risk Class III or IV at Screening (see PORT Risk Class calculation in Appendix 5).
- 7. Radiographically-confirmed pneumonia, ie, new or progressive pulmonary infiltrate(s) on chest X-ray (CXR) or chest computed tomography (CT) scan consistent with acute bacterial pneumonia within 48 hours prior to the first dose of test article.

- 8. Is expected to require a minimum of at least 2 days of iv therapy for the initial treatment of CABP.
- 9. Females must have a negative pregnancy test at Screening and agree to comply with using an acceptable method of birth control as per your local requirements (eg, abstinence, po contraceptive, intrauterine device [IUD], barrier contraception [condom], tubal ligation, hysterectomy, bilateral oophorectomy, postmenopausal or vasectomized partner) from Screening through PTE. Males must agree to use an acceptable method of birth control with female partner(s) and must not donate sperm from Screening through PTE.

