#### 8.5 Vital Signs

Vital signs including BP, heart rate, respiratory rate, pulse oximetry and body temperature will be measured at the timepoints as specified in Appendix 1. Additionally, BP and heart rate should be measured within 30 minutes before, and approximately 1 hour ( $\pm$  15 minutes) after the completion of the infusions on Day 1 and Day 2.

The subject's BP and heart rate should be captured after at least 5 minutes (+ 5 minutes) of rest while in a non-standing position (supine or semi-recumbent, head of bed from  $0^{\circ}$  to  $90^{\circ}$ ). Subsequent vital sign measurements should be captured in the same non-standing position.

Systolic and diastolic BP will be measured using an automated calibrated device, with an appropriately sized cuff.

Heart rate will be measured using an automated calibrated device, when available. If not available, heart rate will be measured manually.

Temperature will be obtained using an electronic (rapid reading) device whenever possible and the same device should be used for all study assessements.

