6.1.4.1 Diagnosis of CABP

To be included in the CE-EOT and CE-PTE populations, subjects must meet the following protocol defined inclusion criteria that describe the CABP:

Inclusion Criterion 3: Has at least 3 of the following symptoms:

- Cough
- Production of purulent sputum
- Dyspnea (shortness of breath)
- Pleuritic chest pain.

Inclusion Criterion 4: Has at least 2 of the following abnormal vital signs:

- Fever or hypothermia documented by the investigator (po or rectal temperature > 38.0°C [100.4°F] or < 36.0°C [95.5°F])
- Hypotension with systolic blood pressure (SBP) < 90 mmHg
- Heart rate > 90 bpm
- Respiratory rate (RR) > 20 breaths/minute.

Inclusion Criterion 5: Has at least 1 clinical sign or laboratory finding associated with CABP:

- Hypoxemia Partial pressure of arterial oxygen (PaO₂) < 60 mmHg by arterial blood gas (ABG)
- Physical examination findings of pulmonary consolidation (dullness on percussion, bronchial breath sounds, egophony, rales, rhonchi, or decreased breath sounds)
- An elevated total white blood cell (WBC) count (> 12,000 cells/mm³) *or* leucopenia (WBC < 4,000 cells/mm³) *or* elevated immature neutrophils (> 15% band forms regardless of total peripheral WBC count).

Inclusion Criterion 6: Has disease categorized as being PORT III or IV at Screening

Inclusion Criterion 7: Radiographically-confirmed pneumonia, ie, new or progressive pulmonary infiltrate(s) on chest X-ray (CXR) or chest computed tomography (CT) scan consistent with acute bacterial pneumonia within 48 hours prior to the first dose of test article.

The Sponsor Medical Monitor will also review those subjects with a concomitant illness identified after baseline that could have presented at baseline as pneumonia, including COVID-19. If it is determined that the subject does not have pneumonia but had another condition such as lung cancer or COVID-19 at baseline, the subject will not be evaluable for the CE populations. Any subject who is confirmed or suspected to have severe acute respiratory syndrome coronavirus 2 (SARS-CoV-2) infection based on local standard-of-care assessments during the post-randomization period may be excluded from the CE populations based on Sponsor review.

6.1.4.2 **Prior Antibiotic Therapy**

Subjects will be excluded from the CE populations if they meet the prior antibiotic exclusion criteria:

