6.3 Subgroups

Analyses will be conducted (as described in Section 9) for subgroups defined by the randomization stratification factors: PORT Risk Class (III and IV) and receipt of an allowed antibacterial therapy in the 72 hours prior to study treatment (yes vs no). Analyses of ECR (in the ITT population) and clinical response at the PTE visit (in the ITT and CE-PTE populations) will also be conducted in the following subgroups: bacteremic subjects, defined as subjects with a positive blood culture at baseline (microITT population), by CURB-65 Score, and subjects meeting the systemic inflammatory response syndrome (SIRS) criteria at baseline. CURB-65 Score is derived from the eCRF data and ranges from 0-5 where 1 point is given for each of the following at baseline: confusion, blood urea nitrogen > 19 mg/dL (urea > 6.8 mmol/L), respiratory rate \geq 30 breaths/min, systolic blood pressure < 90 mmHg or diastolic blood pressure \leq 60 mmHg, and age \geq 65 years. Confusion is defined as altered mental status as recorded on the PORT Risk Class Determination eCRF. SIRS is defined as having 2 or more of the following criteria: temperature < 36°C or > 38°C (oral or oral equivalent), heart rate > 90 bpm, respiratory rate > 20 breaths/min, or WBC count < 4000 cells/mm³ or > 12,000 cells/mm³ or > 10% bands.

Exploratory analyses in other subgroups may also be conducted.

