Baseline assessments of clinical symptoms, clinical signs, abnormal vital signs, and abnormal laboratory signs of CABP will be presented for the ITT, Safety, microITT, and CE-PTE populations. The number and percentage of subjects with each of the CABP symptoms (cough, pleuritic chest pain, dyspnea, and phlegm/sputum production) by severity (absent, mild, moderate, severe) will be presented by treatment group. The number and percentage of subjects with the presence by severity (ie, absent, mild, moderate, severe) of the following clinical signs will be provided by treatment group: rales, rhonchi, dullness on percussion, bronchial breath sounds, wheezing, decreased breath sounds, and egophony. The number and percentage of subjects with fever (defined as body temperature > 38°C [100.4°F] oral or rectal), hypothermia (defined as body temperature < 36°C [95.5°F] oral or rectal), hypotension with systolic blood pressure < 90 mmHg, heart rate > 90 bpm, respiratory rate > 20 breaths/min, hypoxemia (defined as PaO₂ < 60 mmHg by arterial blood gas or

oxygen saturation < 90% by pulse oximetry), elevated total WBC count (> 12,000 cells/mm³), leucopenia (WBC < 4,000 cells/mm³), elevated immature neutrophils (> 15% band forms regardless of total peripheral WBC count) and any of elevated total WBC count, leucopenia or elevated immature neutrophils will be summarized by treatment group. Differences between treatment groups will be tested for statistical significance using Fisher's exact test.

Risk factors for CABP will be presented by treatment group for the ITT, Safety, microITT, and CE-PTE populations. Risk factors include smoking (current, past, and descriptive statistics of the number of years since quitting for those subjects who were previous smokers), receipt of pneumococcal vaccine, prior lung infection, whether the subject had mild to moderate COPD, symptomatic asthma with wheezing, and chronic cough with or without sputum production. Differences between treatment groups will be tested for statistical significance using Fisher's exact test for categorical variables and the Wilcoxon rank sum test for continuous variables. Other medical and surgical history will be summarized based on MedDRA system organ class by treatment group for the ITT and Safety populations.

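### SAP 6.1.4.1 adds an oral-or-rectal limit to Inclusion 4 that the protocol does not contain, so some correctly enrolled subjects could fail the CE and ME definitions

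*SAP*

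**What the plan says.** SAP 6.1.4.1 opens the CE definition by saying that "subjects must meet the following protocol defined inclusion criteria that describe the CABP". It then lists "Inclusion Criterion 4: Has at least 2 of the following abnormal vital signs", the four being temperature, systolic pressure, heart rate and respiratory rate. The temperature item begins "Fever or hypothermia documented by the investigator (po or rectal temperature".

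The protocol's own criterion, in section 6.2 and identically in the synopsis, reads "Fever or hypothermia documented by the investigator (temperature > 38.0°C [100.4°F] or < 36.0°C [95.5°F". The thresholds are the same and no route is given. The only measurement rule is in Protocol 8.5: "Temperature will be obtained using an electronic (rapid reading) device whenever possible", with the same device to be used throughout. No body site is required.

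The SAP uses two temperature conventions elsewhere. The baseline table in SAP 8.2 counts "fever (defined as body temperature > 38°C [100.4°F] oral or rectal", and treats hypothermia likewise. The SIRS definition in SAP 6.3, repeated in 8.2, accepts "oral or oral equivalent" readings.

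**The concern.** A rule presented as the protocol's own is stricter than the protocol. A subject can be correctly enrolled on a temperature taken by a route other than oral or rectal and then fail the SAP's version of the same criterion. The exclusion would turn on how temperature was taken, not on whether the subject had CABP.

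Two populations are involved. CE is defined directly by this rule. ME is the overlap of microITT and CE (SAP 6.1.5), so a CE loss carries into ME for subjects with a baseline pathogen. Protocol 12.6.3 requires non-inferiority in both ITT and CE for the EMA. In the present SAP the CE-PTE and ME-PTE results are secondary and descriptive (SAP 9.3).

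The baseline tables have a related, smaller problem. One reading accepted as an oral equivalent can count toward SIRS but not as fever in the same section.

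**Working it through.** **1. The texts side by side**

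| Place | Route required |
|---|---|
| Protocol 6.2 and synopsis, Inclusion 4 | none |
| Protocol 8.5, measurement rule | none (device type only) |
| SAP 6.1.4.1, Inclusion 4 for CE | oral or rectal |
| SAP 8.2, fever and hypothermia rows | oral or rectal |
| SAP 6.3 and 8.2, SIRS | oral or oral equivalent |

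**2. Who is exposed**

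The criterion needs two of four signs.

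- Qualifying temperature by another route, plus exactly one of SBP < 90, HR > 90 or RR > 20: two signs under the protocol, one under the SAP. Eligible, but fails CE.
- Qualifying temperature by another route, plus two or more of the other signs: meets both versions. Stays in CE.

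The loss among subjects who meet Inclusion 4 is therefore

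loss = (share measured by another route) × (share needing temperature to reach two signs).

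**3. Possible size of the second factor**

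The documents give no sign frequencies, so these are assumptions, with the signs taken as independent:

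share needing temperature = P(temperature) × P(exactly one other sign) / P(at least two of four).

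- Temperature 80%, SBP 5%, HR and RR 90% each: 0.80 × 0.1715 / 0.9562 = 14.3%.
- Temperature 70%, SBP 3%, HR and RR 60% each: 0.70 × 0.4704 / 0.70368 = 46.8%.

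Two intermediate sets gave 20.3% and 21.9%. If another route was used in 10% of subjects (assumed), the loss is 1.4% to 4.7%. If it was used in 50% (assumed), the loss is 7.2% to 23.4%.

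**4. The plan's own CE power, reproduced**

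Inputs from SAP 5.1.1: N = 670 × 0.80 = 536, or 268 per arm; success 89% in both arms; margin 0.10; one-sided alpha 0.025; Farrington-Manning.

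- Restricted estimates under a difference of −0.10: 0.8228 and 0.9228.
- SE0 = √[(0.8228 × 0.1772 + 0.9228 × 0.0772)/268] = 0.02846.
- SE1 = √[2 × 0.89 × 0.11/268] = 0.02703.
- Power = Φ[(0.10 − 1.96 × 0.02846)/0.02703] = Φ(1.636) = 94.9%, as stated.

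**5. The same formula after assumed further losses from CE**

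| Further loss | CE N | Power |
|---|---|---|
| 0 | 536 | 94.9% |
| 1% | 531 | 94.7% |
| 5% | 509 | 93.8% |
| 10% | 482 | 92.6% |
| 20% | 429 | 89.4% |

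These rows show sensitivity. They do not predict the loss.

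**The case against.** The strongest reply is that the mechanism is not shown to operate. SAP 6.2.2 sets CE membership by program from eCRF data together with a manual review by the blinded Evaluability Review Team. Nothing in the documents says that the eCRF records route, or that any site used another route. If route is not captured, no program can apply the limit. Because SAP 6.1.4.1 calls its criteria protocol defined, a reviewer would also have grounds to apply the protocol's version. This stands, and it makes the consequence conditional. It does not remove the need to correct the text: a rule that cannot be applied as written, or that a reviewer must override, should not define a population.

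A second reply is that Protocol 12.3 lets the SAP add evaluability criteria. It does, but this limit is presented as the protocol's criterion, and no reason for it is given. The next item points to incomplete reconciliation: the SAP's Inclusion 5 omits the pulse-oximetry limb and adds examination findings not in the protocol's list.

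A third reply is that SIRS is a separate construct and may have its own temperature rule. That is fair.

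Several stronger readings are tempting, but the documents do not support them:

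- *Everyone whose fever was measured another way is excluded.* Only those who need that temperature to reach two signs are exposed, and ME is touched only for those in microITT (planned at 30%, 201 of 670).
- *The EMA co-primary analysis is compromised.* SAP section 3 puts the EMA analyses in a separate SAP, and whether it carries the same wording is unknown.
- *Losses cluster by site or country.* The documents give no route data.
- *The treatment comparison is biased.* Screening temperature precedes 1:1 randomization, so exclusion on its route should not by itself favour an arm.

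**Conclusion.** The discrepancy is real and plain on the text. SAP 6.1.4.1 limits Inclusion 4 to oral or rectal temperature; the protocol does not. If route is captured and the rule is applied literally, a subject who reaches two signs only through another route is eligible but fails CE-EOT and CE-PTE, and ME if in microITT.

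The size cannot be determined, because the documents give neither the mix of routes nor the sign frequencies. Even an assumed 20% loss leaves CE power at 89.4%, close to the 89.6% planned for the FDA primary endpoint. The ITT analysis does not use this rule and is unaffected. No CE or ME result in this SAP supports a non-inferiority conclusion. The point is therefore a population definition that should be made to match the protocol. It is not a threat to the primary result.

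**What to change.** Delete *po or rectal* from the temperature item in SAP 6.1.4.1, so that the CE test equals Protocol Inclusion 4 as applied at enrolment. Use the same route-free definition for the fever and hypothermia rows in SAP 8.2. Putting the SIRS convention in those rows instead would leave a reading that counts for CE but not as fever. The SIRS definition in SAP 6.3 and 8.2 may stay as it is if labelled as a separate convention. Check whether the EMA SAP carries the same limit and, if so, correct it too.

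The cost is SAP wording only. No new data are needed, and the planned CE N of 536 and power of 94.9% do not change. The change should be made before the blinded population classification is finalised, which SAP 6.2.2 places ahead of database lock.

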### Main Criteria for Inclusion:

- 1. Written and signed informed consent must be obtained before any protocol specific assessment is performed.
- 2. Male or female, aged 18 years or older.
- 3. Has at least 3 of the following symptoms:
  - Cough
  - Production of purulent sputum
  - Dyspnea (shortness of breath)
  - Pleuritic chest pain
- 4. Has at least TWO of the following abnormal vital signs:
  - Fever or hypothermia documented by the investigator (temperature > 38.0°C [100.4°F] or < 36.0°C [95.5°F])
  - Hypotension with SBP < 90 mm Hg
  - Heart rate > 90 beats per minute (bpm)
  - RR > 20 breaths/minute
- 5. Has at least 1 clinical sign or laboratory finding associated with CABP:
  - Hypoxemia (PaO2 < 60 mm Hg by ABG or oxygen saturation < 90% by pulse oximetry)
  - Physical examination findings of pulmonary consolidation (eg, dullness on percussion, bronchial breath sounds, or egophony)
  - An elevated total white blood cell (WBC) count (> 12,000 cells/mm^3) or leucopenia (WBC < 4,000 cells/mm^3) *or* elevated immature neutrophils (> 15% band forms) (regardless of total peripheral WBC count)
- 6. Has disease categorized as being PORT Risk Class III or IV at Screening (see PORT Risk Class calculation in Appendix 5).
- 7. Radiographically-confirmed pneumonia, ie, new or progressive pulmonary infiltrate(s) on chest X-ray (CXR) or chest computed tomography (CT) scan consistent with acute bacterial pneumonia within 48 hours prior to the first dose of test article.
- 8. Is expected to require a minimum of at least 2 days of iv therapy for the initial treatment of CABP.
- 9. Females must have a negative pregnancy test at Screening and agree to comply with using an acceptable method of birth control as per your local requirements (eg, abstinence, po contraceptive, intrauterine device [IUD], barrier contraception [condom], tubal ligation,

hysterectomy, bilateral oophorectomy, postmenopausal or vasectomized partner) from Screening through PTE. Males must agree to use an acceptable method of birth control with female partner(s) and must not donate sperm from Screening through PTE.

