## Appendix 1Schedule of Events

Study Phase	Screening b	i Trea	iv 1tment				iv o	r po T	reatm	ent					EOT a	and Follo	ow-up f
Study David	-1	1	2	3	. 4	5	6	7 d	8	9	10	11	12	13	EOT e	PTE	FFU f
Study Day					inpatient only	t	inpatient only		inp	atient		in	patient	only			
						ECP visit			0	nly	1:6					5 4- 10	
					r	nust occur 7	2		co	ntinuin	g and t	this is 1	not the	nt is EOT		days after	30 to
					←	to 120 hours	s →		11	visit. Ti	eatmen	nt past	10 days	s is		last day	after
					6	c	,c		anov	ved for	Scre	ening.	bacter	emia at		therapy	Day 1
Screening and eligibility procedures					I										1		
Signed informed consent g	Х																
Medical history, current medical conditions, demography	X																
Assessment of CABP symptom	x		x	x	x	x	x	x	x	x	x	x	x	x	x	x	
severity n								21				21					
Chest X-ray or CT scan 	X					-											-
PORT risk class, ABG (or pulse oximetry) j	Х																
Sample collection for local SARS-	x																
CoV-2 molecular testing																	
Blood and urine samples for local lab hematology/chemistry/pregnancy k	Х																
SF-36v2 ® Health Survey	Х																Х
Review of Inclusion/Exclusion criteria	Х																
Randomization (if Eligible)		Х															
Clinical Procedures and Test Article A	Administration	n															
Test article administration and		x	x	x	x	x	x	x	x	x	x	x	x	x			
accountability									~	21							
Physical examination m	X		X	Х	X	X	X	X			X				X		
Vital signs n	Х	Xo	Xo	Х	Х	Х	Х	Х	Х	X	X	X	Х	Х	X		
12-lead ECG w	Х														X		
Blood for central lab tests:	Хр					x									Xp	Xp	
hematology/chemistry/pregnancy																	
AEs, SAEs, and mortality q	X	Х															Х
Prior & concomitant medications r	X	Χ															Х

Plasma samples (in heparin) for PK analyses s		Х				Х											
Study Phase	Screening b	Trea	iv tment				iv o	r po T	reatm	ent					EOT a	nd Follo	w-up f
Study Day a	-1	1	2	3	4 inpatient only	5	6 inpatient only	7 d	8 inpati	9 ent only	10	11 inp	12 atient c	13 only	EOT e	PTE	FFU f
Assessment for po switch or need for continued therapy t				Х	[									X			
Investigator's Assessment of Clinical Response															Х	Х	

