- Subjects should receive their first dose of test article within 4 hours after randomization. The total duration of test article therapy (iv plus po) for all subjects will be 7-10 days (up to 14 days for subjects with bacteremia identified at Screening). The pharmacist or designee will be unblinded to prepare appropriate iv doses of the IxRS identified test article. An unblinded field monitor will perform drug accountability and review the pharmacist's records. Oral test article may be dispensed and reconciled by blinded or unblinded personnel. All oral doses should be taken in a fasted state (no food, antacids or multivitamins containing multivalent cations [eg, aluminum, magnesium, calcium, bismuth, iron, or zinc] or drink except water for at least 4 hours before dosing). After dosing, no food is permitted for 2 hours as well as no dairy products, antacids, or multivitamins containing multivalent cations (eg, aluminum, magnesium, calcium, bismuth, iron, or zinc) for 4 hours. Subjects discharged with po test article will be asked to return all unused test article and packaging at each visit. At the EOT visit subjects discharged with po test article will return any remaining unused po test article and site staff will perform accountability.
- m A full physical examination will be completed at Screening. Thereafter, abbreviated physical examinations may be performed at the indicated timepoints. Additional physical examinations may be performed as clinically indicated.
- n Vital signs include body temperature, BP, pulse oximetry, heart rate, and RR.
- o Blood pressure and heart rate should be measured within 30 minutes before, and approximately 1 hour (± 15 minutes) after the completion of the infusions on Day 1 and Day 2.
- pBlood will be collected from all female subjects for a serum β-hCG pregnancy test at the Central Laboratory at the Screening, EOT and PTE visits.
- qAEs and SAEs will be recorded from the time of signing of the ICF to the Final Follow-up assessment.
- r Medications administered within the 7 days prior to the date of signing the ICF or during the Screening phase will be recorded in the eCRF, as will all medications and significant non-drug therapies administered after the first dose of test article.
- s PK sample collection to occur on Day 1 (2 to 3 hours after the start of Dose 1) and at the ECR visit (Days 4 to 6; at any time during the visit).

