- 4. Congestive heart failure is defined as systolic or diastolic ventricular dysfunction documented by history, physical examination, and chest radiograph, echocardiogram, multiple gated acquisition scan, or left ventriculogram. Subjects with unstable cardiac disease (including acute congestive heart failure) within the 3 months prior to Screening should not be enrolled per Exclusion Criterion number 6.
- 5. Cerebrovascular disease is defined as a clinical diagnosis of stroke or transient ischemic attack or stroke documented by magnetic resonance imaging or CT.
- 6. Renal disease is defined as a history of chronic renal disease or abnormal blood urea nitrogen and creatinine concentrations documented in the medical record. Subjects with history or evidence of severe renal disease or who have a calculated creatinine clearance (CrCl) of < 30 mL/minute, or who require any form of dialysis should not be enrolled per Exclusion Criterion number 9.
- 7. Altered mental status is defined as disorientation with respect to person, place, or time that is not known to be chronic, stupor, or coma.
- 8. In cases where the arterial blood gas (ABG) test is not collected as part of hospital routine, no points should be added during PORT score calculation. If ABG test results are available, please ensure that arterial pH value is taken into account for PORT risk class calculation.

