A table will provide the frequency counts and percentages by treatment group for subjects who received prior antibiotics (as randomized), PORT Risk Class (from the eCRF and as randomized), CURB-65 Score, subjects meeting the modified American Thoracic Society (ATS) severity criteria, and subjects meeting the SIRS criteria for the ITT, microITT and CE-PTE populations. PORT score will also be summarized as a continuous variable. CURB-65 score is derived from the eCRF data and ranges from 0-5 where 1 point is given for each of the following at baseline: confusion, blood urea nitrogen > 19 mg/dL(urea > 6.8 mmol/L), respiratory rate \geq 30 breaths/min, systolic blood pressure < 90 mmHg or diastolic blood pressure ≤ 60 mmHg, and age ≥ 65 years. Confusion is defined as altered mental status as recorded on the PORT Risk Class Determination eCRF. Modified ATS severity and SIRS criteria are derived from the eCRF data. Modified ATS severity criteria is defined as presence of ≥ 3 of the following 9 criteria at baseline: respiratory rate \geq 30 breaths/min, O₂ saturation < 90% or PaO₂ < 60 mmHg, blood urea nitrogen \geq 20 mg/dL, $WBC < 4000 \text{ cells/mm}^3$, confusion, multilobar infiltrates, platelets $< 100,000 \text{ cells/mm}^3$, temperature $< 36^{\circ}$ C, and systolic blood pressure < 90 mmHg. SIRS criteria is defined as having 2 or more of the following 4 symptoms at baseline: temperature $< 36^{\circ}$ C or $> 38^{\circ}$ C (oral or oral equivalent), heart rate > 90 bpm, respiratory rate > 20 breaths/min, WBC $< 4000 \text{ cells/mm}^3$ or WBC $> 12,000 \text{ cells/mm}^3$, or bands > 10%. Differences between treatment groups will be tested using Fisher's exact test for categorical variables and the Wilcoxon rank sum test for continuous variables.

By-subject listings of the modified ATS severity criteria and SIRS criteria will be provided. A listing of subjects with discrepancies between the PORT Risk Class to which they were randomized and their true PORT Risk class as captured in the clinical database will also be provided.

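### SAP 6.1.4.1 omits the pulse-oximetry route from Inclusion Criterion 5, so the CE and ME populations do not follow the protocol criterion they claim to apply

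*SAP*

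**What the plan says.** **The CE rule.** SAP 6.1.4.1 states that CE-EOT and CE-PTE subjects must satisfy the inclusion criteria defined in the protocol that describe the pneumonia, and then lists Criteria 3 to 7. Under Criterion 5 the hypoxemia item reads "Hypoxemia Partial pressure of arterial oxygen (PaO₂) < 60 mmHg by arterial blood gas (ABG"). No saturation alternative follows.

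**The protocol criterion.** Inclusion Criterion 5 in the protocol synopsis and in Section 6.2 accepts PaO2 below 60 mm Hg "by ABG or oxygen saturation < 90% by pulse oximetry".

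**Elsewhere in the SAP.** Section 8.2 defines baseline hypoxemia with the alternative "oxygen saturation < 90% by pulse oximetry", and its modified ATS severity item reads "O₂ saturation < 90% or PaO₂ < 60 mmHg".

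**What is measured.** The Screening row of Protocol Appendix 1 is "PORT risk class, ABG (or pulse oximetry"). Note n of that appendix states "Vital signs include body temperature, BP, pulse oximetry, heart rate, and RR", and vital signs are scheduled at Screening. Protocol Appendix 5, note 8, gives a scoring rule for use "In cases where the arterial blood gas (ABG) test is not collected as part of hospital routine".

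**What depends on the rule.** SAP 6.1.5 defines each ME set as the overlap of microITT and the matching CE set. SAP 6.2.2 assigns CE membership by program from the eCRF together with manual review by the Evaluability Review Team (ERT).

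**The concern.** The SAP presents the list as the protocol's own, yet one of the two accepted ways to show hypoxemia is missing. The retained route depends on an optional test, while the dropped one uses a scheduled measurement. The same subject could therefore be counted as hypoxemic in the SAP 8.2 baseline table and fail the hypoxemia item for CE.

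What is at stake is whether CE-EOT, CE-PTE, ME-EOT and ME-PTE are the populations the SAP says they are. A correctly enrolled subject could be dropped for lack of a blood gas the trial never required.

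The printed list also differs from Inclusion Criteria 4 and 5 in two places not marked as changes:

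- The chest signs are "dullness on percussion, bronchial breath sounds, egophony, rales, rhonchi, or decreased breath sounds". The protocol names only the first three, as examples.
- Criterion 4 carries an oral or rectal route for temperature. The protocol criterion names no route.

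**Working it through.** **1. Criterion 5 compared route by route**

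| Finding | Protocol 6.2 | SAP 6.1.4.1 |
|---|---|---|
| PaO2 < 60 mm Hg (ABG) | accepted | accepted |
| Saturation < 90% (oximetry) | accepted | absent |
| Dullness, bronchial breath sounds, egophony | accepted | accepted |
| Rales, rhonchi, decreased breath sounds | not named (list is by example) | accepted |
| WBC > 12,000 or < 4,000, or bands > 15% | accepted | accepted |

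**2. Where the two rules disagree.** Treat each row as yes or no, which gives 2^5 = 32 combinations. A rule accepts a combination if at least one of its listed findings is present.

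- *If the protocol's examples do not cover the added signs (assumption):* the protocol ignores that row and rejects 2 combinations, so it accepts 32 − 2 = 30. The SAP ignores the saturation row and also accepts 30. They differ in 2: saturation alone is lost and the added signs alone are gained.
- *If the examples do cover them:* the protocol rejects only the all-negative combination and accepts 31. The SAP accepts 30. They differ in 1: saturation alone is lost.
- *With the saturation clause restored:* the SAP accepts 31 and rejects nothing the protocol accepts, under either reading.

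These are combinations, not frequencies, and they cover Criterion 5 only. The temperature route in Criterion 4 lies outside the table.

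**3. Scale.** The documents give no count of affected subjects. The only planning figure for CE is in Protocol Table 4 and SAP 5.1.1: N = 0.80 × 670 = 536 (268 per arm), 89% success in both arms, margin 10%, 1-sided alpha 0.025, power 94.9%.

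The Farrington-Manning formula is power = Φ[(0.10 − 1.96·s0)/s1]. Here s0 uses the success rates constrained to differ by 0.10 (0.8228 and 0.9228), and s1 uses 0.89 in both arms.

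- s0 = √[(0.8228 × 0.1772 + 0.9228 × 0.0772)/268] = 0.02846
- s1 = √[2 × 0.89 × 0.11/268] = 0.02703
- (0.10 − 1.96 × 0.02846)/0.02703 = 1.636, so power = 94.9%, as stated

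If an assumed further share of CE were lost, power would be:

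| Assumed extra CE loss | N | Power |
|---|---|---|
| 1% | 531 | 94.7% |
| 5% | 509 | 93.9% |
| 10% | 482 | 92.6% |
| 20% | 429 | 89.4% |

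The losses are assumptions shown for range, and nothing in the documents supports any one of them. The problem is who belongs to the population, not power.

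**4. Related slips in the 72 to 120 hour summary (descriptive only)**

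- *WBC.* SAP 9.4 and Protocol 12.8 both join the limits below 12,000 and at least 4,000 by or. Every WBC value meets at least one of them. Joined by and, only 4,000 to 11,999 passes.
- *Bands.* SAP 9.4 adds bands below 15% by and. If the two form a joint item, it then rests on bands alone: WBC 20,000 with 10% bands counts as stabilised, and WBC 8,000 with 20% bands does not. Protocol 12.8 joins bands by or, so both count.
- *Oxygen.* SAP 9.4 attributes a PaO2 above 60 mmHg to oximetry or ABG. Protocol 12.8 pairs PaO2 of at least 60 with ABG, and saturation of at least 90% with oximetry.

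**5. Temperature pair (editorial).** The hypothermia limit is printed as 36.0°C and 95.5°F. But 36.0 × 9/5 + 32 = 96.8°F, and (95.5 − 32) × 5/9 = 35.28°C.

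**The case against.** The best defence is that this is an incomplete transcription of a named protocol criterion, not a new ABG-only rule. SAP 6.1.4.1 refers to the protocol and gives the criterion number, SAP 8.2 keeps the saturation route twice, and the ERT may in practice apply the full criterion. SAP 6.2.1 gives the ERT a role in determining the criteria used, under a process document not supplied here. Protocol 12.3 also leaves further evaluability criteria to the SAP. Finally, only a narrow profile is lost, and from analyses that are descriptive in this SAP.

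Part of this stands. Actual misclassification is not shown, and the effect may be small. The rule uses baseline findings and applies to both arms, so there is no obvious directional bias. The chest-sign difference is soft because the protocol's list is by example, and the oral or rectal wording recurs in SAP 8.2 and may be a convention. The WBC wording could be meant as resolution of whichever abnormality was present, although it does not say so.

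The central point survives. A transcription error is still an error in the text to be programmed. Nothing in SAP 6.2 tells the ERT to apply saturation; its review confirms the written criteria. The latitude in Protocol 12.3 does not explain a list labelled as the protocol's own.

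**Conclusion.** The concern holds. As printed, SAP 6.1.4.1 does not reproduce Inclusion Criterion 5, and a correctly enrolled subject with saturation below 90% as the sole qualifying finding would be excluded from CE and ME. Confidence in the text mismatch is high. Whether any subject was in fact misclassified is unknown, because it requires the SAP to be applied literally and such subjects to exist.

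Neither the number affected nor the net direction for CE size can be derived. Within Criterion 5 the two rules disagree on at most two profiles; a real restriction on temperature route would add a further difference under Criterion 4.

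The ECR primary analysis in ITT is unaffected. SAP 9.3 and 9.4 make the CE and ME intervals descriptive. CE is co-primary for the EMA, but SAP Section 3 places that analysis in a separate SAP that was not supplied, so carry-over cannot be judged. This should be fixed, but it does not threaten the primary result. The chest-sign, temperature, WBC and oxygen items are secondary and add no weight to that rating.

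**What to change.** **Main change.** In the hypoxemia item of SAP 6.1.4.1, add the alternative of oxygen saturation below 90% by pulse oximetry. State separately whether the wider chest-sign list and the oral or rectal temperature route are intended departures from the protocol. Confirm that the EMA SAP contains the saturation route.

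**Secondary changes**

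- In SAP 9.4, and in Protocol 12.8 at its next amendment, join the two WBC limits by and.
- Reconcile the connective before immature neutrophils between the two documents, and say whether WBC and bands belong in the SAP summary, whose sentence names only vital signs.
- Restore the Protocol 12.8 oxygen item in SAP 9.4.
- Reconcile the Celsius and Fahrenheit hypothermia limits wherever they appear.

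**Cost.** A short SAP revision and a few lines of derivation code, with no new data. The SAP is V5.0 final, with approvals dated 29 May to 5 June 2024, so a new version and re-approval are needed. Changes to Protocol 12.8 or Criterion 4 need a written amendment.

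Protocol 12.1 requires population decisions and final SAP approval before database lock, but the documents give no lock date. If lock has not happened, correct the text first. If it has, report how CE membership was actually derived.
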